8.2.2. NEWS

The median time to discharge or to a NEWS of ≤ 2 and CI will be summarized by treatment group (Table 36). The hazard ratio and log rank p-values will be provided with the summaries. Differences in time-to-event endpoints by treatment arm will be summarized with Kaplan-Meier curves. Number at risk, hazard ratio and log rank p-values will be included on the figures (Figure 15).

The mean, standard deviation (SD), median, minimum, and maximum NEWS at Baseline and Study Visit (not necessarily actual) Days 3, 5, 8, 11, 15 and 29 will be presented by treatment arm as well as change from baseline at each post-Day 1 visit (Table 39). A figure with mean and SD over time will also be presented by treatment arm (Figure 16).

Subject listings of NEWS responses (overall and individual components) by day will be generated (Listing 6).

8.2.3. Days of Oxygenation

Duration of oxygenation days will be summarized in a table using medians and quartiles by treatment arm (Table 41). This will only include subjects in category 5, 6, or 7 at enrollment. Analyses will be performed in the ITT population, Treated population, and a subset of the

Treated population of treated subjects only as subjects who are not treated are terminated from the study immediately and are included in the ITT/Treated analyses with a count of 1 day. Bee swarm plots of oxygen days by treatment arm will be generated, where subject whose days are imputed to the maximum of 28 days due to death are grouped separately from subjects who do not die (Figure 17).

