7. STUDY INTERVENTION DISCONTINUATION AND SUBJECT DISCONTINUATION/WITHDRAWAL

7.1 Halting Criteria and Discontinuation of Study Intervention

7.1.1 Individual Infusion Halting

See Section 6.1.4. for information about dosing modifications due to laboratory abnormalities.

For an individual subject, an individual infusion must be stopped if they have a suspected drug-related event of hypersensitivity (Grade 2 or higher) during the infusion. While there are no criteria

for grading “hypersensitivity” in the Division of AIDS (DAIDS) Table for Grading the Severity of Adverse Events, sites should use acute allergic reaction from that toxicity table. Subjects who have an IV infusion stopped for a safety related issues will not continue with dosing.

The treatment of any given subject may be stopped for SAEs, clinically significant adverse events, severe laboratory abnormalities, or any other medical conditions that indicate to the Investigator that continued dosing is not in the best interest of the patient.

In addition, a subject in this clinical study may discontinue study drug at their request for any reason. Every effort should be made to encourage subjects to remain in the study for the duration of their planned outcome assessments. Subjects should be educated on the continued scientific importance of their data, even if they discontinue study drug.

Unless the subject withdraws consent, those who discontinue study drug early will remain in the study. The reason for subject discontinuation of study drug should be documented in the case report form.

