The overall eligibility of the subject to participate in the study will be assessed once all screening values are available. Complete the Eligibility Checklist on day of enrollment as this form includes data needed to register all potential subjects in the Advantage eClinical system. The

screening process can be suspended prior to complete assessment at any time if exclusions are identified by the study team.

Study subjects who qualify will be randomized in the Advantage eClinical system, and all others will be registered as screen failures. The study team has 24 hours to complete Day 1 baseline assessments prior to the first infusion including the collection of OP swab and blood, assessment of the ordinal scale and NEWS and completing or recording a baseline physical examination that was done.

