9.3 Populations for Analyses

The primary analysis will be based on an intention-to-treat population, including all subjects randomized. Similarly, safety analyses will be based a modified intent-to-treat population consisting of all subjects who received at least one infusion. The primary analysis will be based on those subjects enrolled in order to 400 recoveries. Subsequent analysis will be performed on all enrolled subjects.

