3.3.2. Recovery and Time to Recovery

The primary efficacy outcome measure is the time to recovery. Recovery will be defined as having a value of 1, 2, or 3 on the clinical status 8-point ordinal scale. The time to recovery will be defined as the elapsed time (in days) from randomization to the earliest day at which a subject reaches recovery. Note that since clinical status assessments are recorded as defined in Section 4.3, the day that is being assessed (not necessarily the day the response is collected) will be used to determine the timing of events. For example, a subject with a score of 5 recorded on Days 1 - 3 and a score of 3 recorded on Day 4 will have a time to recovery equal to 3 days. It is also possible that a subject has a clinical status score > 3 reported for a particular day but was subsequently discharged on the same day. For these scenarios where a subject is discharged with no reported clinical score of 1, 2, or 3 will be considered recovered at the time of discharge.

Any subjects that are lost to follow-up or terminated early prior to an observed recovery will be censored at the day of their last observed assessment. Subjects who complete follow-up but do not experience recovery will be censored at the day of their Day 29 visit. All deaths within Day 29 (and prior to recovery) will be considered censored at 28 days. Note that we do not expect many subjects to worsen after discharge.

However, we will evaluate whether any discharged subjects subsequently experience a worse clinical status and sensitivity analyses will be conducted accordingly. For these analyses, subjects who recover but are later re-admitted will not be considered a recovery but will instead be censored at 28 days. Sensitivity analyses will be performed where subjects who were crossover treated with remdesivir (per April 29, 2020 Protocol Administrative Letter) will be censored at the time of remdesivir treatment initiation. In addition, the analyses will be replicated where subjects who were unblinded, regardless of whether they received crossover treatment of remdesivir or not, will be censored at the time of unblinding.

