6.3.1. Intention-to-Treat (ITT) and Treated Populations

The intent-to-treat (ITT) population includes all subjects who were randomized.

The treated population includes all randomized subjects who received any study drug infusion, even if the infusion was halted or slowed.

For the main analyses of the primary and secondary efficacy outcomes, subjects in both populations will be classified by the treatment arm and disease severity stratum to which they were randomized. For safety, subgroup, and sensitivity analyses, subjects may be classified by their randomized or actual disease severity and placebo subjects who cross over and are treated with remdesivir will be censored/excluded as described in Section 3 and Section 8.

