9.4. Deaths, Serious Adverse Events and other Significant Adverse Events

A listing of death and other serious adverse events will be presented, including Subject ID, treatment group, Adverse Event Description, Associated Dose Number, Number of Days Post Dose (Duration), Number of Days Post Dose the Event Became Serious, Reason Reported as an SAE, Severity, Relationship to Treatment, Alternate Etiology if not Related, Action Taken with

Study Treatment, Subject Discontinuation, Outcome, MedDRA SOC, and MedDRA PT (Listing 12 and Listing 13).

The number of subjects who die by Day 15 and Day 29 will be presented by treatment arm. The 14- and 28-day crude mortality rate, which will use the number of subjects in the treatment group and analysis population as the denominator, will be presented (Table 59). The analysis will be repeated censoring placebo subjects who were retreated with remdesivir at the time of retreatment.

Mortality through Day 15 and 29 will also be analyzed as a time to event endpoint (see Section 3.3). A table will present median time to event along with 95% confidence intervals overall for each treatment arm along with the hazard ratio estimate and log rank p-values (Table 61). Differences in time-to-event endpoints by treatment will be summarized with Kaplan-Meier curves (Figure 23). Analyses of mortality will be performed in the ITT and the Treated analysis populations and will be performed on both the early and the full analysis sets.

The ITT tabular summaries will be repeated censoring placebo subjects who were retreated with remdesivir at the time of retreatment. Similarly, the summaries will be repeated censoring subjects who were unblinded at the time of unblinding.

Rates of Grade 3 and 4 AE occurrence will be compared between treatment arms using Barnard's exact test and presented (Table 63). Rates of SAE occurrence will also be compared between treatment arms using Barnard's exact test and presented. Further, the composite endpoint of the occurrence of death, SAE, or Grade 3 or 4 AE described in Section 3.3 will be analyzed as a time to event outcome. A table will present median time to event along with 95% confidence intervals overall for each treatment arm along with the hazard ratio estimate and log rank p-values (Table 64). Differences in time-to-event endpoints by treatment will be summarized with Kaplan-Meier curves (Figure 24).

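### Randomized subjects who are never infused leave follow-up at once, so the all-randomized recovery analysis rests in effect on infused subjects

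*SAP*

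**What the plan says.** Both documents define the primary population by randomization alone. Protocol 9.3: "The primary analysis will be based on an intention-to-treat population, including all subjects randomized". SAP 6.3.1: "The intent-to-treat (ITT) population includes all subjects who were randomized". SAP 8.1.1 runs the primary recovery analysis in that population.

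The handling of subjects who never receive an infusion appears only in the secondary analyses. SAP 8.2.3 says that "subjects who are not treated are terminated from the study immediately" and are "included in the ITT/Treated analyses with a count of 1 day". The same statement recurs in 8.2.5, 8.2.7 and 8.2.9.

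Three other rules decide what happens to such a subject:

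- SAP 3.3.2: subjects "terminated early prior to an observed recovery will be censored at the day of their last observed assessment". SAP 6.5 repeats this for time-to-event outcomes in general.
- SAP 9.4 plans a crude 14- and 28-day mortality rate, "which will use the number of subjects in the treatment group and analysis population as the denominator".
- SAP 3.3.10 classifies an early-terminated subject as dead if a death before Day 29 becomes known.

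On conduct, Protocol 8.1.1 randomizes first and then says: "The study team has 24 hours to complete Day 1 baseline assessments prior to the first infusion". Protocol 7.1.1 says of those who stop treatment: "Unless the subject withdraws consent, those who discontinue study drug early will remain in the study".

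**The concern.** An ITT analysis protects the randomized comparison only if outcomes are collected on everyone randomized. Subjects can be in the ITT list and still contribute nothing if follow-up ends on the day they enter. The interval between randomization and first infusion makes an uninfused group foreseeable, and the SAP plainly expects one. Non-infusion is settled after randomization and may be related to prognosis.

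No protocol section provides for ending follow-up because no infusion was given. Protocol 7.1.1 speaks of stopping drug rather than never starting it, but its reason for continued follow-up, the value of the outcome data, applies equally.

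At stake are the meaning of the ITT label on the primary result, the completeness of Day 15 status and vital status, and much of the value of setting ITT beside Treated results as a consistency check (SAP 8.1.2 and 8.2). None of the sensitivity analyses specified in SAP 8.1.2 addresses uninfused subjects.

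**Working it through.** **1. The plan's own figures reproduce.** For a rate ratio of 1.35, two-sided 0.05 and 85% power, E = 4(1.96 + 1.036)² / (ln 1.35)² = 399, against 400 stated (Protocol 9.2, SAP 5). Sample size at 70% recovery (Protocol 9): 400 / 0.70 = 571.4, so 572, as stated. The point disputes neither figure.

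**2. One uninfused subject followed through the rules.**

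- *Recovery:* terminated at once, so the last observed assessment is about Day 1 and censoring falls there.
- *Day 15 status:* Protocol 9.4.3 excludes subjects without final outcome data. The SAP 6.5 imputation rules for this endpoint cover only discharged or readmitted subjects, so a terminated inpatient has no value.
- *Crude mortality:* in the denominator; in the numerator only if a death is recorded or learned of.
- *Recovery and death summary (SAP 8.1.2 and its table shell):* the categories are recovered, not recovered and died. There is none for unknown status.

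**3. Effect on the log-rank test.** In the SAP 8.1.1 statistic, a subject censored before the first recovery time is in no risk set and adds nothing to O, E or V. As a check, one simulated, unstratified data set of 572 subjects (286 per arm, rate ratio 1.35, 406 recoveries) was used. To it were added 30 uninfused subjects, 10 on remdesivir and 20 on placebo (30/602 = 5%).

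| Handling of the 30 | Z |
|---|---|
| Left out | 3.291 |
| Censored at day 0 | 3.291 |
| Censored at day 1 | 3.308 |
| Held as not recovered to day 28 | 3.708 |

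The first three rows are practically one analysis. The last row depends on the assumed 10 to 20 split, but shows that the handling can matter when arms differ.

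**4. Effect on size and power.** Let u be the uninfused share, which the documents do not give; assume 1% to 5%. Of 572 subjects that is 5.7 to 28.6. To reach 400 recoveries, N = 572/(1 − u):

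| u | N for 400 recoveries | Recoveries if N stays 572 | Power |
|---|---|---|---|
| 1% | 578 | 396 | 84.8% |
| 2% | 584 | 392 | 84.4% |
| 3% | 590 | 388 | 84.1% |
| 5% | 603 | 380 | 83.3% |

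Because recruitment is tied to 400 recoveries, power is not the issue.

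**5. Effect on crude mortality.** If uninfused subjects die at the common rate m and none of their deaths becomes known, the crude rate is m(1 − u), understated by m × u.

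- m = 2% (Day 15 control deaths, Scenario 1, Protocol 9.2): 0.02 points at u = 1% and 0.10 points at u = 5%.
- m = 10% (assumed): 0.1 to 0.5 points.

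In relative terms this is u, or 1% to 5%. If uninfused subjects die at k times the rate of the others, the relative shortfall is uk / (1 − u + uk), roughly k times u when u is small.

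**6. Imbalance by arm, no true effect.** The crude risk ratio is the ratio of the (1 − u) terms. At 1% versus 3% it is 0.99/0.97 = 1.02; at 0% versus 5% it is 1/0.95 = 1.05.

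**7. Width of a bounding analysis.** With all uninfused taken as alive the rate is m(1 − u); with all taken as dead it is m(1 − u) + u. At m = 2% the bounds are 1.98% and 2.98% for u = 1%, and 1.90% and 6.90% for u = 5%.

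**The case against.** The case for leaving this alone has real substance.

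- **The effect is probably small.** The share is unknown, blinding favours balance between arms, and the primary test is event-driven. Material bias needs imbalance or prognostic selection that the documents do not show. This stands.
- **The scale will be visible.** The SAP's population table counts uninfused subjects by arm and severity, and a listing gives reason and day of early termination. This stands, but it shows how many outcomes are missing without supplying any.
- **The conflict with Protocol 7.1.1 is indirect.** It covers stopping rather than never starting, and the no-replacement rule in 7.2 is limited to subjects who received product. Some uninfused subjects may have withdrawn consent, and for them ending follow-up is proper. This stands, and the remedy must respect it.
- **ITT and Treated recovery results are not identical.** The Treated analysis in SAP 8.1.2 also censors subjects ineligible at baseline at enrollment. So the comparison is not empty, but it tells nothing about the uninfused.
- **Prospective follow-up is too late here.** SAP 3.0 cites an article of May 22, 2020. A subject randomized on April 20, the last permitted day, reached Day 29 on May 18.

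A reader might also infer three stronger things, which the documents do not support:

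- That subjects found ineligible after randomization go uninfused and are terminated. No section says this. The only rule for them places them in the Treated population, which presupposes an infusion.
- That deaths before the first infusion lose their outcome. Protocol 8.3.5 records SAEs from consent and 8.3.2 counts death as one. SAP 3.3.2 and 8.1.1 give a death before recovery the worst rank.
- That uninfused subjects are simply counted as survivors. SAP 3.3.10 reclassifies deaths learned of and censors the others in the time-to-death analysis. Only the crude rate is exposed. SAP 3.3.10 is written for time to death, and the SAP does not say whether it governs the crude rate. Nor is any active retrieval of vital status planned.

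**Conclusion.** The point holds in a limited form. The SAP's own statement, made four times, that uninfused subjects leave at once means that an analysis defined on all randomized subjects carries almost no outcome information on part of them. For recovery the main cost is loss of a true ITT analysis, not loss of power. For crude mortality the understatement is up to about 1% to 5% in relative terms (0.02 to 0.10 percentage points at 2% mortality). That rests on an assumed 1% to 5% uninfused share, the same death rate as other subjects, and no later knowledge of their deaths. Deaths learned of reduce it; sicker uninfused subjects increase it, and unequal numbers by arm distort the comparison. Censoring at about Day 1 is inferred from two rules read together. The change is worth making because it is cheap and restores what the ITT label promises, not because a large bias has been shown.

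**What to change.** 1. **This stage, data.** For uninfused subjects, where consent allows, retrieve discharge date, ordinal status and vital status through Day 29 by phone or chart. Use them in the ITT recovery, Day 15 and mortality analyses. The protocol's schedule of assessments already allows phone collection of ordinal status, readmission and mortality.
2. **This stage, analysis.** Add to SAP 8.1.2 and 9.4 an ITT bounding sensitivity analysis for uninfused subjects whose outcome stays unknown. For recovery: not recovered to Day 29, and recovered at Day 1. For mortality: died, and alive.
3. **SAP wording.** Correct 8.2.3, 8.2.5, 8.2.7 and 8.2.9, which place uninfused subjects in the Treated analyses although SAP 6.3.1 excludes them from that population.
4. **Later stages.** State in Protocol 7.1 and 7.2 that a randomized but uninfused subject stays in follow-up for outcomes unless consent is withdrawn.

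The cost is minor site effort for what is probably a small number of subjects, a few added table rows and short wording changes.

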8.2.4. Incidence of New Oxygen use

The incidence and duration of new oxygen use will be analyzed by treatment arm. This will only include subjects in category 4 at enrollment. New use will be identified by a post-enrollment score of at least 5; the number of subjects reporting new use and the incidence rate (and CI) will be reported.

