8.1.2.1 Measures of clinical support, limitations and infection control

The subject's clinical status will be captured on each study day while hospitalized and on Day 15 and 29 if hospitalized or the subject returns for an in-person clinic visit. It will also be captured on Day 22 during a phone visit. Clinical status is largely measured by the ordinal scale and the NEWS. Unlike the NEWS, the ordinal scale can also be evaluated over the phone if the discharged subject is unable to return for visits on Day 15 and 29 as well as on Day 22.

Ideally, complete the ordinal scale concurrently with the NEW Score just prior to infusion, as time permits. The following measures are recorded for the ordinal scale:

- Hospitalization.
- Oxygen requirement.
- Non-invasive mechanical ventilation (via mask) requirement.
- High flow oxygen requirement.
- Invasive mechanical ventilation (via endotracheal tube or tracheostomy tube) requirement.
- ECMO requirement.
- Ongoing medical care preventing hospital discharge (COVID-19 related or other medical conditions).
- Limitations of physical activity (self-assessed).
- Isolated for infection control purposes.

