8.1.2.2 Ordinal Scale

The ordinal scale is the primary measure of clinical outcome.

The scale used in this study is as follows (from worst to best):

- Death;
- Hospitalized, on invasive mechanical ventilation or ECMO;
- Hospitalized, on non-invasive ventilation or high flow oxygen devices;
- Hospitalized, requiring supplemental oxygen;

- Hospitalized, not requiring supplemental oxygen - requiring ongoing medical care (COVID-19 related or otherwise);
- Hospitalized, not requiring supplemental oxygen - no longer requires ongoing medical care;
 - This would include those kept in hospital for quarantine/infection control, awaiting bed in rehabilitation facility or homecare, etc.
- Not hospitalized, limitation on activities and/or requiring home oxygen;
- Not hospitalized, no limitations on activities

To determine a subject's clinical status using the ordinal scale: On Day 1, report their clinical status at randomization. On Day 2, report the period from randomization to midnight on Day 1. On Day 3 through Day 11, or until discharged, and on Days 15, 22 and 29, provide the worst clinical assessment for the previous day (i.e., midnight to midnight; 00:00 – 23:59 (24-hr clock)). For example, on study Day 3 when completing the form, the worse clinical outcome measure of Day 2 is captured with the worst being death followed by ECMO, mechanical ventilation, etc. The Day 2 measurement is assessed as occurring anytime in that 24-hour period (00:00 to 23:59).

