3. STUDY OBJECTIVES AND ENDPOINTS

3.1. Study Objectives

Primary Objective

The overall objective of the study is to evaluate the clinical efficacy of different investigational therapeutics relative to the control arm in patients hospitalized with COVID-19 as assessed by the time to recovery up to Day 29.

Secondary Objectives

The key secondary objective is to evaluate the clinical efficacy of different investigational therapeutics relative to the control arm in patients hospitalized with COVID-19 as assessed by the 8-point ordinal clinical status scale at Day 15.

The other secondary objectives are to:

1. Evaluate clinical efficacy of different investigational therapeutics as compared to the control arm as assessed by:
 - Clinical Severity
 - 8-Point Clinical Status Ordinal scale:
 - Time to an improvement of one category and two categories from Day 1 (baseline) on the clinical status 8-point ordinal scale.
 - Subject clinical status using 8-point ordinal scale at Days 3, 5, 8, 11, 15, 22, and 29.
 - Mean change in the clinical status 8-point ordinal scale from Day 1 to Days 3, 5, 8, 11, 15, and 29.
 - National Early Warning Score (NEWS):
 - Time to discharge or to a NEWS of ≤ 2 and maintained for 24 hours, whichever occurs first.
 - Change from Day 1 to Days 3, 5, 8, 11, 15, and 29 in NEWS.
 - Oxygenation:
 - Days requiring oxygen through Day 29.
 - Incidence and duration of new oxygen use through Day 29.
 - Non-invasive ventilation/high flow oxygen:
 - Days of non-invasive ventilation/high flow oxygen through Day 29.
 - Incidence and duration of new non-invasive ventilation or high flow oxygen use through Day 29.
 - Invasive Mechanical Ventilation / extracorporeal membrane oxygenation (ECMO):
 - Days of ventilator/ECMO through Day 29.

- Incidence and duration of new mechanical ventilation or ECMO use through Day 29.
 - Hospitalization
 - Duration of hospitalization (in days) through Day 29.
 - Mortality
 - 14-day mortality.
 - 28-day mortality.
2. Evaluate the safety of the intervention through 28 days of follow-up as compared to the control arm as assessed by:
- Cumulative incidence of SAEs through Day 29
 - Cumulative incidence of Grade 3 and 4 clinical and/or laboratory AEs through Day 29.
 - Discontinuation or temporary suspension of infusions (for any reason).

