3.3.8. Days of Oxygen

Oxygen days will be defined as the number of days where the clinical status score is equal to 5, 6, or 7. After discharge, the CRF question regarding days of oxygenation will be used. The total number of days will be the sum of all reported days, regardless of whether the days occur consecutively or in disjoint intervals. See Section 6.5 for the plan for handling subjects who do not have data through Day 29 or die prior to Day 29.

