Table 1: Categories of the NEWS scale.

PHYSIOLOGICAL PARAMETERS	3	2	1	0	1	2	3
Respiration Rate	≤8		9 - 11	12 - 20		21 - 24	≥25
Oxygen Saturations	≤91	92 - 93	94 - 95	≥96			
Any Supplemental Oxygen		Yes		No			
Temperature	≤35.0		35.1 - 36.0	36.1 - 38.0	38.1 - 39.0	≥39.1	
Systolic BP	≤90	91 - 100	101 - 110	111 - 219			≥220
Heart Rate	≤40		41 - 50	51 - 90	91 - 110	111 - 130	≥131
Level of Consciousness				A			V, P, or U

Oxygenation, Non-invasive ventilation/high flow oxygen, Invasive Mechanical Ventilation / extracorporeal membrane oxygenation (ECMO), hospitalization and mortality will be assessed using results of the 8-point ordinal scale and post discharge eCRF questions.

Safety will be assessed by the following:

- Cumulative incidence of serious adverse events (SAEs) through 28 days of follow-up.
- Cumulative incidence of Grade 3 and 4 AEs.
- Discontinuation or temporary suspension of infusions (for any reason)
- Changes in white cell count, absolute neutrophil count, hemoglobin, platelets, creatinine, glucose, total bilirubin, ALT, AST, and PT over time.

Clinical labs will be drawn on Days 1, 3, 5, 8, 11 and on Day 15 and 29 if the subject is able to return to the clinic or is still hospitalized.

Virologic efficacy is an exploratory endpoint and will be assessed by the following:

- Qualitative and quantitative PCR for SARS-CoV-2 in OP swab on Days 1; 3, 5, 8, 11 (while hospitalized); and Day 15 and 29 (if able to return to clinic or still hospitalized).
- Qualitative and quantitative PCR for SARS-CoV-2 in blood on Days 1; 3, 5, 8, 11 (while hospitalized).

The schedule of study procedures is provided in [Table 2](#) below.

Table 2: Schedule of Study Procedures (from protocol version 3.0)

Day +/- Window	Screen	Baseline	Study Intervention Period	Follow-up Visits			
	-1 or 1	1	Daily until hospital discharge	15 ⁷ ± 2	22 ⁷ ± 3	29 ⁷ ± 3	
ELIGIBILITY							
Informed consent	X						
Demographics & Medical History	X						
Targeted physical exam	X						
Review SARS-CoV-2 results	X						
STUDY INTERVENTION							
Randomization		X					
Administration of remdesivir or control		Daily until discharge or 10 days. No study product given after Day 10.					
STUDY PROCEDURES							
Vital signs including SpO ₂		X ⁴	Daily until discharge	X ⁷	X ⁷	X ⁷	
Clinical data collection ¹		X ⁴	Daily until discharge	X ⁷	X ⁷	X ⁷	
Adverse event evaluation		X ⁴	Daily until discharge	X ⁷	X ⁷	X ⁷	
Concomitant medication review		X ⁴	From Day -7 to Day 11				
SAFETY LABORATORY							

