8.2.6. Incidence of New Non-Invasive Ventilation/High-Flow Oxygen

The incidence and duration of new Non-Invasive Ventilation/High-Flow Oxygen use will be analyzed by treatment arm. This will only include subjects in category 4 or 5 at enrollment. The incidence of new oxygen use will be analyzed by treatment arm. This will only include subjects in category 4 at enrollment. New use will be identified by a post-enrollment score of at least 6. The number of subjects reporting new use and the incidence rate (and CI) will be reported.

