8.2.8. Incidence of New Non-Invasive Ventilation/High-Flow Oxygen

The incidence and duration of new Non-Invasive Ventilation/High-Flow Oxygen use will be analyzed by treatment arm. This will only include subjects in category 4, 5, or 6 at enrollment. The incidence of new oxygen use will be analyzed by treatment arm. This will only include

subjects in category 4 at enrollment. New use will be identified by a post-enrollment score of 7. The number of subjects reporting new use and the incidence rate (and CI) will be reported.

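### SAP 8.2.4, 8.2.6 and 8.2.8 define new support by the ordinal score alone, against SAP 4.3 and the day-count rules: oxygen first started at home can never count, while a death without support can.

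*SAP*

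**What the plan says.** The objective in SAP 3.1 is "Incidence and duration of new oxygen use through Day 29", with parallel objectives for non-invasive ventilation/high-flow oxygen and for invasive ventilation/ECMO.

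The incidence rules are:

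- SAP 8.2.4 (category 4 at enrollment): "New use will be identified by a post-enrollment score of at least 5".
- SAP 8.2.6 (category 4 or 5): "New use will be identified by a post-enrollment score of at least 6".
- SAP 8.2.8 (category 4, 5 or 6): "New use will be identified by a post-enrollment score of 7". This section carries the non-invasive heading, but its score and its baseline categories show that invasive ventilation/ECMO is meant.

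None of the three names a second data source. SAP 4.3 does: it states that oxygenation, both kinds of ventilatory support, hospitalization and mortality "will be assessed using results of the 8-point ordinal scale and post discharge eCRF questions". The day counts follow 4.3. For oxygen, SAP 3.3.8 says "After discharge, the CRF question regarding days of oxygenation will be used", and 3.3.6 and 3.3.7 say the same of a question on days of ventilation.

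On timing, Protocol 8.1.2.1 says "clinical status will be captured on each study day while hospitalized". For discharged subjects Protocol 8.1.2.2 asks sites to score at the visits only: "and on Days 15, 22 and 29, provide the worst clinical assessment for the previous day". SAP 3.2 places home oxygen in category 2 and death in category 8.

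**The concern.** The incidence rule and the duration rule for the same objective draw on different data. Two programmers could produce different incidence figures, one reading 8.2.4 alone and the other reading it with 4.3. Table 41 sets new-use incidence and days on oxygen side by side for subjects not on oxygen at baseline, so a subject can contribute oxygen days there and still not be a new user.

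The loss also depends on length of stay. Scores are daily in hospital and sparse afterwards, and the treatment is expected to shorten the stay. A rule that sees less after discharge could therefore lose more events in the arm that leaves hospital sooner and flatter that arm.

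**Working it through.** **No stated figure for this outcome.** The documents give no rate, power or sample size for new use. The one design value borrowed below is the recovery rate ratio of 1.35. The formula in SAP section 5 gives 4(1.96 + 1.036)² / (ln 1.35)² = 35.91 / 0.0901 ≈ 399 recoveries, against the stated 400, so that input reproduces.

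**What the score can see after discharge.** Scores of 3 to 7 are all hospitalized states, so a subject at home scores 1 or 2. Oxygen first started at home is caught 0% of the time, whatever its length. This affects 8.2.4 only.

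For readmissions, suppose scoring happens only at Days 15, 22 and 29, on the nominal days. The days described are then 14, 21 and 28. After discharge on Day 7, Days 8 to 28 remain: 21 days, 3 of them scored. With onset spread evenly over those 21 days:

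| Length of readmission on support | Onset days that overlap Day 14, 21 or 28 | Caught |
|---|---|---|
| 1 day | 3 of 21 | 14% |
| 3 days | 9 of 21 | 43% |
| 5 days | 15 of 21 | 71% |
| 7 days | 21 of 21 | 100% |

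If daily scoring resumes on readmission, nothing in this table is missed and only home oxygen is lost.

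**Effect on the arm difference (illustration; all values assumed except 1.35, which stands in for speed of discharge).** Discharge is exponential with median 8 days on control and 1.35 times the rate on remdesivir. The daily probability of first use is 3% in hospital and r × 3% after discharge, equal in both arms. In-hospital starts are always seen. Extra difference = missed on remdesivir − missed on control.

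| r | Post-discharge use | Control true / by rule | Remdesivir true / by rule | Missed, control vs remdesivir | Extra difference (points) |
|---|---|---|---|---|---|
| 0.1 | 3-day readmissions | 30.2% / 27.8% | 26.3% / 23.4% | 2.4 vs 2.9 | 0.4 |
| 0.1 | all home oxygen | 30.2% / 26.1% | 26.3% / 21.5% | 4.1 vs 4.7 | 0.6 |
| 0.25 | 3-day readmissions | 35.9% / 30.0% | 32.8% / 25.9% | 5.9 vs 6.9 | 1.0 |
| 0.25 | all home oxygen | 35.9% / 26.1% | 32.8% / 21.5% | 9.7 vs 11.3 | 1.5 |

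(Missed values and differences were taken before rounding.) With control medians of 5, 8 and 11 days the extra difference is 0.4 to 0.6 points at r = 0.1, 0.9 to 1.5 at r = 0.25, and 3.0 to 4.8 at r = 1. The last would mean that discharged subjects start support as often as inpatients.

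A second illustration assumes a control median stay of about 6 days, 2% per day in hospital, and a flat 5% readmitted on oxygen for 2 to 7 days. True incidence is 19.0% vs 16.1%, a difference of 2.9 points. By the rule it is 17.4% vs 14.4%, a difference of 3.0. Each arm loses about 1.6 to 1.7 points, and the contrast moves by 0.1.

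**The opposite error.** Death is 8, and 8 ≥ 6 ≥ 5. A death with no preceding oxygen counts as new use in 8.2.4, and one with no non-invasive or invasive ventilation counts in 8.2.6. It does not count in 8.2.8, where the score must be 7. The net direction of error in 8.2.4 and 8.2.6 is therefore not fixed.

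**Nothing elsewhere repairs it.** SAP 6.5 imputes 7 for a readmission without a score, but only for the key secondary outcome.

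**The case against.** The strongest reply is that 8.2.4 does not say the score is the sole source and can be read together with 4.3. That would make this a wording gap and not a biased analysis. It is a fair account of the intent, but an analyst who follows the three sections as written would use the score and nothing else.

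A reader might also infer that every readmission on oxygen between visits goes unseen. The documents do not support that. Protocol 8.1.2.1 has status captured on each day in hospital, and a readmitted subject is in hospital. The schedule of assessments, by contrast, has clinical data collected daily until discharge and then at visits. The question is open, and on the first reading readmission losses are zero.

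Nor does home oxygen undermine all three sections. It is irrelevant to 8.2.6 and 8.2.8. In 8.2.4 a subject who starts oxygen in hospital and goes home on it already has a qualifying score, so only a first start after discharge is lost.

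Finally, these are secondary summaries in baseline subsets. SAP 8.2.4 plans counts and rates with intervals, SAP 6.8 makes no multiplicity adjustment, and the primary and key secondary analyses are untouched. All of this stands and limits the point's weight. The conflict between sections remains.

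**Conclusion.** The point holds as an internal conflict: data that the SAP already uses to count days of support are not carried into the rule for new support. Two consequences follow from the text with no assumed rates: oxygen first started at home can never count in 8.2.4, and a death without support counts in 8.2.4 and 8.2.6. Missed readmissions are conditional on how readmission days are scored.

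It is tempting to conclude that the rule materially favours remdesivir. That is not supported. The direction follows only if post-discharge use is non-zero and similar between arms. No readmission or home-oxygen rate is given, SAP 3.3.2 expects few subjects to worsen after discharge, and deaths push the count the other way. The distortion of the arm difference is probably under 1 point: 0.1 to 0.6 in the lower-rate illustrations. It exceeds 1 point only if post-discharge use approaches a quarter or more of the inpatient rate. The amendment is worth making because it removes a contradiction at little cost.

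**What to change.** - **8.2.4:** define new use as a post-enrollment score of 5, 6 or 7, or more than 0 post-discharge oxygen days on the eCRF.
- **8.2.6:** a post-enrollment score of 6 or 7. **8.2.8:** a score of 7. Add the post-discharge ventilation question to either only if the eCRF item separates non-invasive/high-flow from invasive/ECMO. SAP 3.3.6 and 3.3.7 refer to it in the same words, so without that separation non-invasive support after discharge could be counted as new invasive ventilation.
- **4.3:** state whether daily scoring resumes on readmission and, if not, how readmission days are classified for these outcomes.

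The cost is SAP wording and programming. Post-discharge answers are partly self-reported. They may also be incomplete: the schedule footnote limits phone visits and all Day 22 visits to adverse events, ordinal status, readmission and mortality. The eCRF is not among the documents, so the sponsor should confirm when the support questions are asked and tabulate by arm how many discharged subjects have no answer.
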